Precision Biotechnology

Protocol Version: PB-2018-V12

Protocol Date: 2022-06-15

Clinical Trial Protocol

Phase I, open-label study to evaluate safety and tolerability of PB101 in combination with standard treatment, EGFR-TKI, in EGFR-mutated advanced non-small cell lung cancer

Investigational Product Name: PB101 Autologous Immune Cell Therapy

Indication: Patients with histologically confirmed EGFR-mutated stage III/IV NSCLC

Study Type: Phase I, single-center, single-arm, open-label study

Protocol ID: PB-2018

Planned Study Start Date: September 2018

Planned Study Early Termination Date: August 2019

Study Completion Date: December 2023

Principal Investigator:

[name], Department of Hematology and Oncology, Taipei Medical University Hospital

Co-Investigators:

[name], Division of Pulmonary and Critical Care Medicine, Department of Internal Medicine, Tri-Service General Hospital, Taipei, Taiwan.

Sponsor: Precision Biotechnology Co., Ltd.

Responsible Person: [name]

Address: [name]

[contact], [name]

E-mail: [contact]

Protocol Synopsis (Cell Therapy)

I . Protocol title:

A Phase I, open-label study to evaluate safety and tolerability of PB101 in combination with standard treatment, EGFR-TKI, in EGFR-mutated advanced non-small cell lung cancer

II . Objectives:

To determine the safety and tolerability of PB101 in combination with standard of care EGFR-TKI in patients with EGFR-mutated advanced non-small cell lung cancer.

III . Test Product:

1. Name: PB101

2. Cell type: NK /NKT Cell

3. Sources: autologous allogeneic homologous use minimal manipulation

Dose(s): two-dose level: 1x10⁹* cells (*allow ± 10% cell number)

4. Dosing schedule: administrative route: intravenous

5. frequency: PB101 infusion weekly for 4 weeks

IV. Developmental phase: phase I II III IV Others First-in-human trial

V . Study design:

1. Control: placebo

active (please specify name and dosage)

other

Uncontrolled

2. Blinding: open-label evaluator blind single blind double blind double dummy other

3. Randomized: yes no

4. Parallel Cross-over Other

5. Duration of treatment: 4 weeks

6. Titration: forced optional none

7. Multi-national Multi-center(Taiwan) Single center

VI. Endpoints**1. Primary endpoint(s):**

1.1 Safety (Phase I) – to determine the dose of PB101 that can be given within dose-limiting toxicities.

2. Secondary endpoints:

To observe the overall response rate (ORR), duration of response (DR) and progression-free survival (PFS).

VII. Selection criteria:**1. Main inclusion criteria:**

1.1 Men and women 20 years of age or older.

1.2 Subjects with histologically or cytologically confirmed stage IIIB/IV non-small cell lung cancer, not amenable to definitive multi-modality therapy, or recurrent disease after a prior diagnosis of stage I-III disease. All staging is via the American Joint Committee on Cancer (AJCC)/IASLC 7th edition proposed staging criteria.

1.3 EGFR sensitizing mutation must be detected in tumor tissue. Specifically, patients harboring the most common mutations, deletions in exon 19 or the L858R mutation in exon 21 are eligible. Other EGFR sensitizing mutations may be eligible after discussion with the principal investigator.

1.4 Subjects must have measurable or evaluable disease according to RECIST v1.1.

1.5 Patients may have had a prior EGFR-TKI including gefitinib, erlotinib, afatinib, or osimertinib in the metastatic setting, but treatment duration must have been less than three months at the time of enrollment.

1.6. Patients may have had no more than one prior line of chemotherapy or immunotherapy in the metastatic setting. At least 14 days must have elapsed from the last chemo/immunotherapy administration until the start of protocol treatment, and patients must have recovered from the side effects of any of these agents.

1.7 Eastern Cooperative Oncology Group (ECOG) performance status of 0, 1, or 2.

1.8 Acceptable organ function, as evidenced by the following laboratory data:

- (1). Aspartate aminotransferase (AST) and alanine aminotransferase (ALT) $\leq 3.0 \times$ upper limit of normal (ULN). (for patients with known hepatic metastases, AST and/or ALT $< 5 \times$ ULN)
- (2). Total serum bilirubin $\leq 1.5 \times$ ULN
- (3). Absolute neutrophil count (ANC) $\geq 1500 \text{ cells/mm}^3$
- (4). Platelet count $\geq 75,000 \text{ cells/mm}^3$
- (5). Hgb $\geq 10.0 \text{ g/dL}$
- (6). Serum creatinine levels $\leq 1.5 \times$ ULN, or calculated (by Cockcroft-Gault formula or other accepted formula) or measure creatinine clearance $\geq 50 \text{ mL/min}$.

2. Main exclusion criteria:

2.1. Patients with history of clinically significant interstitial lung disease or radiation pneumonitis.

2.2. Patients with brain metastasis or leptomeningeal disease.

2.3. Patients who have had radiation to the lung fields within four weeks of starting treatment. For all palliative radiation to all other sites, at least 7 days must have elapsed prior to starting to treatment.

2.4. Patients who have had major surgery (e.g., intra-thoracic, intra-abdominal or intra-pelvic) within two weeks prior to starting study drug or who have not recovered from side effects of such procedure. Video-assisted thoracic surgery (VATS) and mediastinoscopy will not be counted as major surgery and patients can be enrolled in the study ≥ 1 week after the procedure.

2.5 Patients with a second, clinically active, cancer. Patients with second cancers which have been treated with

[figure not shown]
curative intent and/or are currently inactive are allowed.

- 2.6. Known history of human immunodeficiency virus (HIV) seropositivity.
- 2.7. Participants who are receiving any other investigational agents. Patients previously treated with investigational agents must complete a washout period of at least one week or five half-lives, whichever is longer, before starting treatment.
- 2.8. Patients receiving concomitant immunosuppressive agents or chronic corticosteroid use, except those on topical or inhaled steroids, or steroids given via local injection.
- 2.9. Patients with clinically significant, uncontrolled cardiovascular disease, such as: unstable angina or myocardial infarction within 6 months prior to screening, abnormal left ventricular ejection fraction (LVEF <50%), cardiac arrhythmia not controlled with medication, uncontrolled hypertension defined as a SBP \geq 160mm Hg and/or DBP \geq 100mm Hg, with or without anti-hypertensive medication. Initiation or adjustment of antihypertensive medication(s) is allowed prior to screening.
- 2.10. Presence of fungal, bacterial, viral, or other infection requiring IV antimicrobials for management.
- 2.11. Pregnancy and lactating women.
- 2.12. Active hepatitis B or C without treatment.
- 2.13. Other situations the investigators think not eligible for participation in the research.

VIII. Study procedures:

This study will be conducted in one phase. Phase I will investigate safety of PB101. Subjects will be administered 1×10^9 * cells (*allow $\pm 10\%$ cell number) of PB101 over at least 30 minutes weekly for 4 weeks via intravenous infusions, 6 patients will be evaluated. Briefly, after re-visiting to the hospital in 7 ± 3 days to confirm the safety, the subject will continue to be given 1×10^9 cells of PB101 for the following four consecutive weeks.

The schema of PB101 infusion in phase I as shown:

IX. Concomitant treatment:**1. Permitted:**

1.1 Standard of care EGFR-TKIs: Gefitinib (Iressa), Erlotinib (Tarceva), Afatinib (Giotrif), or Osimertinib (Tagrisso)

2. Prohibited:

2.1 There is no absolute contraindication for concomitant medication. However, drugs affecting Iressa, Tarceva, Giotrif or Tagrisso exposure should be noticed.

2.2 Strong inducers of CYP3A4 (e.g., rifampicin, phenytoin, or tricyclic antidepressant) increase the metabolism of Iressa/Tarceva and decrease Iressa/Tarceva plasma concentrations. Increase Iressa or Tarceva daily dose in patients receiving a strong CYP3A4 inducer and resume to standard dose 7 days after discontinuation of the strong inducer.

2.3 Strong inhibitors of CYP3A4 (e.g., atazanavir, clarithromycin, indinavir, itraconazole, ketoconazole, nefazodone, nelfinavir, ritonavir, saquinavir, telithromycin, troleandomycin (TAO), voriconazole, or grapefruit or grapefruit juice) decrease Iressa/Tarceva metabolism and increase Iressa/Tarceva plasma concentrations. A dose reduction should be considered if severe adverse reactions occur.

2.4 Strong CYP3A4 inducer decrease the exposure of Osimertinib and may lead to reduce efficacy of Osimertinib. Avoid coadministering Tagrisso with strong CYP3A4 inducers (e.g., phenytoin, rifampin, carbamazepine, St. John's Wort) [note: effect of St. John's Wort varies widely and is preparation dependent]. Increase the Tagrisso dosage when coadministering with a strong CYP3A4 inducer if concurrent use is unavoidable. No dose adjustments are required when Tagrisso is used with moderate and/or weak CYP3A4 inducers.

2.5 Drugs that elevate gastric pH (e.g., proton pump inhibitors, histamine H2-receptor antagonists, and antacids) may reduce plasma concentrations of Iressa/Tarceva. Avoid concomitant use with proton pump inhibitors, if possible. If treatment with a proton-pump inhibitor is required, take Iressa/Tarceva 12 hours after the last dose or 12 hours before the next dose of the proton-pump inhibitor. Take Iressa/Tarceva 6 hours after or 6 hours before an H2-receptor antagonist or an antacid.

2.6 International Normalized Ratio (INR) elevations and/or hemorrhage have been reported in some patients taking warfarin while on Iressa therapy. Patients taking warfarin should be monitored regularly for changes in prothrombin time or INR.

2.7 Concomitant taking of P-gp inhibitors with Giotrif can increase exposure to afatinib. Reduce Giotrif by 10 mg per day if not tolerated. Co-administration of chronic P-gp inducers orally can decrease afatinib exposure. Increase Giotrif by 10 mg per day as tolerated.

X. Statistics:

1. Primary hypothesis: superiority non-inferiority equivalence other

2. Sample size: 6 evaluable subjects

3. Efficacy population: ITT PP other

Safety population: ITT PP other

4. Statistical method(s) for efficacy/safety evaluations:

In this Phase I trial, 1×10^9 cells/dose of PB101 will be administered to 6 patients. The incidence of DLT events in patients was recorded, and the incidence of DLT would be less than 33% (DLT is defined as the

occurrence of grade ≥ 3 (CTCAE 5.0) adverse reaction related to cell infusion). The observation time of DLT is 28 days after completion of the last PB101 infusion.

5. Planned interim analysis: yes no

XI . Please attach flow chart and/or assessment schedule, if available.

Schedule	Day < -15	Day-15 (± 3)	Day -8 (± 3)	Day -1 (± 3)	Day 0 (± 3)	Day 6 (± 3)	Day 7 (± 3)	Day 14 (± 3)	Day21 (± 3)	Day+28 /End of Treatment/ Withdrawal	Monthly follow up
Informed Consent	V										
Medical/Oncologic History	V										
Physical Examination	V	V	V	V	V	V	V	V	V	V	V
Baseline Signs/Symptoms	V	V	V	V	V	V	V	V	V	V	V
ECOG/body weight/vital signs	V	V	V	V	V	V	V	V	V	V	V
Urinalysis	V										
CBC/DC	V		V	V	V	V	V	V	V	V	V
Blood Chemistry (GOT, GPT, BUN, T-Bil, Cr, UA, Na, K, Ca, Alb)	V				V		V	V	V	V	V
Coagulation (PT,APTT)	V				V						
Tumor markers (CEA)	V				V				V	V	
Thyroid function (TSH, fT4)	V				V			V		V	
Pregnancy Test(Urine)	V										
HIV Test(ELISA)	V										
12-leadECG	V				V			V		V	
Heart echocardiography	V								V		
Bone scan (OPTIONAL)	V										
Tumor imaging (CT or MRI)	V								V	V*	
Tumor Assessments (RECIST1.1)	V								V	V*	
PBMC harvest		V	V	V		V					
Cell infusion					V		V	V	V		
Adverse effect evaluation (CTCAE)	V	V	V	V	V	V	V	V	V	V	
Case report form	01	02	03	04	05	06	07	08	09	10	11, 12

*Done on CRF12

Precision Biotech

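### Does tying the DLT to cell infusion leave the combination objective unanswered when a grade 3 or higher event could be due to both PB101 and the EGFR-TKI?

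*Protocol*

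**What the plan says.** Protocol, II. Objectives, sets the aim: "To determine the safety and tolerability of PB101 in combination with standard of care EGFR-TKI". VI. Endpoints, item 1.1, words the primary endpoint around the cell product alone: "to determine the dose of PB101 that can be given within dose-limiting toxicities". VIII. Study procedures agrees with the endpoint: "Phase I will investigate safety of PB101".

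X. Statistics, item 4, defines a DLT as "occurrence of grade ≥ 3 (CTCAE 5.0) adverse reaction related to cell infusion", observed until 28 days after the last infusion. It says of the 6 patients that "the incidence of DLT would be less than 33"%.

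The EGFR-TKI appears as background. IX. Concomitant treatment, item 1.1, permits any of four standard-of-care agents. VII. Selection criteria, item 1.5, allows earlier TKI use, but "treatment duration must have been less than three months at the time of enrollment". The assessment schedule in XI ticks a CTCAE-based adverse effect evaluation at every visit through the Day+28 column. The protocol names no causality scale and no rule for events with two possible causes.

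**The concern.** The objective is about a combination, while the only quantitative safety criterion counts events by their link to one component. Grade 3 or higher events put down to the TKI alone fall outside the count, and nothing says how an event plausibly due to both is classed. Such events are foreseeable: prior TKI exposure is capped at three months, so the DLT window can overlap early TKI treatment. With one open-label arm, no control group helps to separate the causes.

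The count is also small. Each patient is worth 16.7 percentage points and the criterion turns between one and two DLTs. If the classing of a mixed event is left to judgement after the event is known, the same data could be reported as meeting or missing the criterion.

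**Working it through.** **The criterion.** Inputs from section X: n = 6, incidence below 33%.

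- 0/6 = 0%: met.
- 1/6 = 16.7%: met (exact 95% interval 0.4% to 64.1%).
- 2/6 = 33.3%: not met (exact 95% interval 4.3% to 77.7%).

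The criterion therefore means at most one DLT. The protocol gives no assumed DLT rate, error level or power, so there is no sample-size figure to reproduce.

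**When one mixed-cause patient matters.**

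- No other DLT: 0/6 becomes 1/6, still met.
- Exactly one other DLT: 1/6 becomes 2/6, and the result reverses.
- Two or more other DLTs: already missed, no effect.

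Two mixed-cause patients with no clear DLT would also reverse it (0/6 against 2/6).

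**How often, on assumed rates.** Let pc be the chance that a patient has a clearly infusion-related DLT, and pj the chance of a mixed-cause grade 3 or higher event and no clear one. The documents give neither, so both are assumptions.

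- Criterion met at rate p: P(X ≤ 1) = (1 − p)^6 + 6p(1 − p)^5.
- Result depends on classing, all mixed events counted against none: P(X ≤ 1 at pc) − P(X ≤ 1 at pc + pj).
- Reversal through exactly one mixed patient: 30 · pc · pj · (1 − pc − pj)^4.

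At pc = pj = 10%:

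- Mixed events not counted: 0.5314 + 0.3543 = 0.886.
- Mixed events counted: 0.2621 + 0.3932 = 0.655.
- Difference: 0.230.
- Through one mixed patient: 30 × 0.1 × 0.1 × 0.8^4 = 0.123.

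| pc | pj | Met, mixed not counted | Met, mixed counted | Difference | Through exactly one mixed patient |
|---|---|---|---|---|---|
| 5% | 5% | 96.7% | 88.6% | 8.1% | 4.9% |
| 5% | 10% | 96.7% | 77.6% | 19.1% | 7.8% |
| 5% | 20% | 96.7% | 53.4% | 43.3% | 9.5% |
| 10% | 5% | 88.6% | 77.6% | 10.9% | 7.8% |
| 10% | 10% | 88.6% | 65.5% | 23.0% | 12.3% |
| 10% | 20% | 88.6% | 42.0% | 46.6% | 14.4% |
| 20% | 5% | 65.5% | 53.4% | 12.1% | 9.5% |
| 20% | 10% | 65.5% | 42.0% | 23.5% | 14.4% |
| 20% | 20% | 65.5% | 23.3% | 42.2% | 15.6% |

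The difference column sets two extremes against each other: every mixed event counted, or none. Counting none would mean reading the definition as requiring the infusion to be the sole cause, which it does not say.

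**The wording.** The objective, the primary endpoint and the DLT definition are compatible when read together. PB101 is the product under test, the TKI is standard background treatment, and the question is whether this PB101 dose can be given on top of it. A DLT related to the PB101 infusion, in patients meant to be on a TKI, answers that question. An event produced by the two together is related to the infusion and is inside the definition.

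**The case for a change.** The strongest case for a change is that the protocol itself fixes the DLT and its threshold, so which events qualify is part of the primary endpoint and not a detail for the SAP. The criterion turns on one patient, CTCAE grades severity and does not assign cause, and an open-label investigator would be classing the event with the running count in view. One sentence would settle it: count events at least possibly related to PB101, alone or with the TKI, and report all grade 3 or higher events beside the DLT count.

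Part of this stands. Joint causation is covered by the ordinary sense of related, but merely possible causation is not spelled out, and a sentence saying so would be harmless as a clarification.

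The rest does not carry a required change. Excluding only events clearly due to the TKI alone needs the same unblinded judgement, so the boundary moves without disappearing. Widening the DLT count while keeping 33% raises the question of whether that threshold still suits the wider count, which is debatable. The all-cause tabulation is ordinary safety reporting from evaluations already scheduled. Section X, item 4 attaches no stated consequence to the criterion, and the exact intervals for 1/6 and 2/6 overlap over most of their length. The imprecision therefore comes mainly from having 6 patients.

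**Conclusion.** No change is needed. The definition is consistent with the PB101-focused endpoint and does not shut out combination toxicity. Nothing in the protocol shows that attribution would lean in either direction, or that following the text as written gives a wrong result. The real gap is narrow: how events of uncertain cause are classed is not written down. Investigators and analysts routinely settle this when assessing causality, and listing all grade 3 or higher events beside the DLT count would let readers see any effect of attribution.

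On size, one mixed-cause patient changes the result only at the step from 1/6 to 2/6. Over assumed rates of 5% to 20% for each kind of event, that occurs in 4.9% to 15.6% of trials. The range of 8.1% to 46.6% for all mixed events counted against none is an upper comparison between two extreme readings. Both ranges depend wholly on assumed rates. The conclusion rests on reading related in its ordinary sense and on the protocol alone, since the SAP was not available.

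### The DLT window closes at about Day 49, but the last scheduled CTCAE evaluation is at a Day+28 visit whose starting point is not stated

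*Protocol*

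**What the plan says.** DLT is the primary endpoint: section VI, item 1.1 gives the aim as "to determine the dose of PB101 that can be given within dose-limiting toxicities". Section X, item 4 defines a DLT as an infusion-related adverse reaction of CTCAE 5.0 grade 3 or higher. It expects that "the incidence of DLT would be less than 33" per cent in six patients, and fixes the follow-up for it: "The observation time of DLT is 28 days after completion of the last PB101 infusion".

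The schedule in section XI has eleven columns. The row "Cell infusion" is ticked at Days 0, 7, 14 and 21. The row beginning "Adverse effect evaluation (CTCAE" is ticked in the first ten columns, the tenth being "Day+28 /End of Treatment/ Withdrawal". Its cell in the eleventh column, Monthly follow up, is empty. Five other rows do have a tick there: physical examination, signs and symptoms, ECOG/weight/vital signs, blood count and chemistry.

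The available text gives no reference point for Day+28. Section VIII announces an infusion diagram ("The schema of PB101 infusion in phase I as shown"), but the figure is not in the text at hand and may settle the matter.

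**The concern.** A DLT can be counted only if the event is graded by CTCAE and judged for its relation to the infusion. The schedule should therefore place such an evaluation at or after the end of the DLT window. On one natural reading it does not: the column sequence 0, 7, 14, 21, +28 looks like study days, and the column is also labelled as the end of treatment, which matches section V, item 5 ("Duration of treatment: 4 weeks"). On that reading the last scheduled grading comes one week after the last infusion, three weeks before the window closes.

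The error would run in one direction. Late events that are never graded lower the observed DLT count and make the product look better tolerated. With six patients the result is coarse, and a single event can decide on which side of 33% it falls.

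**Working it through.** **Inputs.** The last infusion is at Day 21 with a visit window of ±3 days (section XI). DLT observation lasts 28 days after it (section X, item 4). The sample is six evaluable patients (section X, item 2), and the criterion is below 33% (section X, item 4).

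**End of the DLT window** = day of last infusion + 28.
- Day 18 + 28 = Day 46
- Day 21 + 28 = Day 49
- Day 24 + 28 = Day 52

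**Reading A: Day+28 is study Day 28.** Days covered = 28 − day of last infusion; days uncovered = 28 − days covered.

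| Last infusion | Window ends | Covered | Uncovered |
|---|---|---|---|
| Day 18 | Day 46 | 10 of 28 (36%) | 18 (64%) |
| Day 21 | Day 49 | 7 of 28 (25%) | 21 (75%) |
| Day 24 | Day 52 | 4 of 28 (14%) | 24 (86%) |

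**Reading B: Day+28 is 28 days after the last infusion.** The visit falls on Day 21 + 28 = Day 49. Coverage is 28 of 28 days, with no shortfall for patients who complete treatment.

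**Which reading does the schedule favour?**
- For A: the weekly sequence of columns; the end-of-treatment label with a four-week treatment duration; and the thyroid and ECG rows, ticked at Days 0, 14 and +28, which is a regular two-week interval if +28 is study Day 28.
- For B: among the dated columns from Day −15 onwards, this is the only one with a plus sign and the only one without ±3; 28 equals the length of the DLT window; and CEA is ticked at both Day 21 and Day+28, a repeat after only 7 days under A but after 28 under B.

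The text does not decide between them.

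**Withdrawal.** The same column serves as the withdrawal visit. A patient seen there d days after the last infusion received, with d below 28, has 28 − d days of the window left and no later scheduled CTCAE evaluation. That gap exists under either reading.

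**What one missed event can do.** 1/6 = 16.7%, which is below 33%; 2/6 = 33.3%, which is not. Missing one event changes the conclusion only when exactly two of the six patients have a DLT. For an assumed true DLT rate p,

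P(X = 2) = 15 · p² · (1 − p)⁴

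- p = 0.05: 15 × 0.0025 × 0.8145 = 0.031
- p = 0.10: 15 × 0.01 × 0.6561 = 0.098
- p = 0.33: 15 × 0.1089 × 0.2015 = 0.329

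These are ceilings for a reversal through one missed event, because one of the two events must also fall after the last grading visit and go unrecorded.

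**Would the first monthly visit close the gap?** Assuming that monthly means 28 to 31 days and is counted from study Day 28, it falls on Day 56 to 59, after the latest window end of Day 52.

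**The case against.** The strongest reply is that nothing here is proven. Under Reading B there is no gap for completers, and the plus sign, the missing ±3, the matching 28 days and the CEA pattern all support B. Pairing the column with withdrawal also fits a count from the last infusion better than a fixed study day. The diagram that is not shown may define the label. **This stands**, and it is why the point is put as an ambiguity. The thyroid and ECG pattern points the other way, however, and a site could follow the label at visits three weeks apart.

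A second reply is that the table may have been damaged in extraction. The starred imaging ticks sit in the column of case report form 10, while their footnote refers to form 12, a monthly follow-up form. **This stands as a caution**: the last two columns need checking against the original. Five rows keep their monthly tick, so the blank CTCAE cell may well be real.

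A third reply is that section X fixes 28 days of observation whatever the visit ticks say, and that monthly examination, symptoms and laboratory tests could reveal late events. **This stands in part.** Such visits may reveal some events, but the grading and causality judgement that make an event a DLT are not scheduled there. The text at hand does not show how events between visits are collected.

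Finally, the 33% figure reads as an expectation with no action attached. That is fair, but it is the only yardstick the protocol gives for its primary endpoint.

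**Conclusion.** The concern holds in its conditional form. The DLT window runs to about Day 49 (46 to 52), and the last scheduled CTCAE evaluation is at a visit with no stated anchor. If that visit is study Day 28, about 21 of the 28 days after the last infusion (18 to 24) have no scheduled grading. If it is counted from the last infusion, completers lose nothing and only the label needs clarifying. Under either reading, a patient seen at the withdrawal visit less than 28 days after an infusion has no later scheduled CTCAE evaluation inside the window.

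This should be fixed, with medium confidence. It rests on the table as extracted, on Day 21 as the last infusion, and on the missing diagram not settling the anchor. One sentence in section VIII could be read as four further weekly infusions after the safety revisit. That would put the last infusion and the window end later and reduce coverage further under Reading A, so sections VIII and XI must be reconciled on this too.

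**What to change.** First check the last two columns of the schedule and the infusion diagram against the original document. Then state what Day+28 is counted from and bring the schedule into line with the DLT window, in one of two ways:

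- anchor the Day+28 visit to the last infusion received; or
- keep it at study Day 28 and tick the CTCAE evaluation at the monthly visit that reaches the end of the window, covering all events since the previous evaluation. On the assumption above, the first monthly visit is enough.

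Whichever is chosen, say that it also applies to patients who withdraw after an infusion, so that their last CTCAE evaluation reaches the end of the 28 days.

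The cost is a relabelled column or one extra tick at an existing visit, plus a sentence of text. No new visit is needed. The downside is slightly more data collection and possibly a less favourable DLT count.

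### Pregnancy is an exclusion, but the only urine test falls before Day -15 in a column with no earliest day, and it is not repeated before any infusion

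*Protocol*

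**What the plan says.** - **Who may enter.** Inclusion 1.1 (Protocol, section VII) admits "Men and women 20 years of age or older", with no upper age and no restriction by child-bearing potential.
- **Who may not.** Exclusion 2.11 reads "Pregnancy and lactating women". It does not say when, or by what test, this is to be established.
- **When it is tested.** In the schedule (section XI) the row "Pregnancy Test(Urine" is marked in the first of eleven columns, Day < -15. The other ten cells are empty.
- **When cells are collected and given.** PBMC harvests are marked at Days -15, -8, -1 and 6. The row "Cell infusion" is marked at Days 0, 7, 14 and 21. All these visits carry a window of ±3 days.
- **What is repeated at Day 0.** CBC/DC, blood chemistry, coagulation, CEA, thyroid function and 12-lead ECG are marked at screening and again at Day 0.

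The text at hand contains no other pregnancy test, no contraception requirement and no limit on the age of screening results.

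**The concern.** An exclusion protects a participant only if it is checked at a time that bears on the exposure. Pregnancy status can change in a few weeks, and a very early pregnancy may not yet show in a urine test. The schedule fixes the only test ahead of the first cell harvest and lets any length of time pass between it and the first infusion. A site that follows the table exactly could infuse a woman who by then meets exclusion 2.11, and could give all four infusions without a further test.

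The participant's safety is at stake, in a trial whose stated objective is safety and tolerability. The sample size of "6 evaluable subjects" and the dose-limiting toxicity criterion are not affected.

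**Working it through.** The plan states no figure to reproduce. The check is a reading of the schedule columns followed by day arithmetic.

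**Inputs (schedule, section XI)**
- Latest day that satisfies Day < -15: Day -16.
- Earliest day that satisfies it: none stated.
- First infusion: Day 0, so Day -3 to Day +3 with the window.
- Fourth infusion: Day 21, so Day 18 to Day 24 with the window.

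**Formula.** Gap = infusion day − test day.

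| Infusion | Nominal | Earliest in window | Latest in window |
|---|---|---|---|
| First | 0 − (−16) = 16 days | −3 − (−16) = 13 days | 3 − (−16) = 19 days |
| Fourth | 21 − (−16) = 37 days | 18 − (−16) = 34 days | 24 − (−16) = 40 days |

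Every entry takes the test on its latest permitted day. For a test on Day −s, with s at least 16, the nominal gaps are s days and s + 21 days. The schedule puts no ceiling on s, so the gaps have no upper limit.

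**Could the row have been misread from the PDF?** This is unlikely. Coagulation, a few rows above, shows marks at screening and Day 0, and the HIV row directly below shows screening only. The table separates one-time from repeated tests, and the pregnancy test stands with the one-time tests.

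**Effect of one added test**
- At Day 0: nominal gaps of 0 days to the first infusion and 21 − 0 = 21 days to the fourth.
- At Day -1: nominal gaps of 0 − (−1) = 1 day and 21 − (−1) = 22 days. If the Day -1 visit falls at the start of its window (Day -4) and the first infusion at the end of its window (Day +3), the first gap is 3 − (−4) = 7 days.

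Either choice puts a ceiling on the gap before the first infusion. Neither re-checks status between the first and the fourth.

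**The case against.** The strongest reply is that the document does not contradict itself. Exclusion 2.11 is an eligibility criterion without a window, the test sits in the eligibility column beside informed consent, and nothing requires eligibility to be re-verified at Day 0. That stands: this is a weakly fixed timing, not two statements that cannot both be true.

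Second, pregnancy is not the only exclusion checked once before treatment. The HIV test (exclusion 2.6) is marked at screening only, and echocardiography (LVEF, exclusion 2.9) at screening and Day 21 only. The contrast with the tests repeated at Day 0 is therefore less sharp than it first looks. It keeps some force, because pregnancy status can change faster than these.

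Third, the early test has a purpose: it comes before the first PBMC harvest. Moving it to Day -1 would leave the Day -15 and Day -8 harvests without any prior test. That is a good reason to add a test and not to move the existing one.

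Fourth, examination and symptoms are recorded at every visit, and exclusion 2.13 leaves room for the investigator's judgement. Clinical review is thus present, but it does not replace a test, and a site that keeps to the table would not retest.

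A reader might also infer more than the document supports:
- *That pregnancy status at the first infusion is simply unknown.* It is known at screening; what is missing is re-confirmation.
- *That 16 and 37 days are strict minima.* They are nominal; with the windows the minima are 13 and 34.
- *That the gap also accounts for exposure to the EGFR-TKI.* The TKI is standard of care, and inclusion 1.5 allows it to have started before enrolment. A test at Day 0 would not prevent that exposure.
- *That a safety failure is shown.* The number of women of child-bearing potential is not given, and the range of 0 to 6 includes none.

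**Conclusion.** The point holds as a gap in timing. The schedule does not secure the plan's own exclusion at the time treatment starts: status goes without re-confirmation for nominally at least 16 days before the first infusion (13 with the window) and at least 37 days before the fourth (34 with the window), with no upper limit on either.

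This rests on two assumptions: that Day < -15 means Day -16 or earlier, and that no further test, contraception rule or limit on the age of screening results stands in trial material not shown here. If such a rule exists, the point shrinks to bringing the schedule into line with it.

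How many participants are affected cannot be derived (0 to 6). The point does not invalidate the trial. It merits a change because the remedy costs almost nothing and serves the trial's stated objective.

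**What to change.** 1. Keep the screening test, which precedes the PBMC harvests.
2. Add a second mark in the urine pregnancy row at the existing Day -1 or Day 0 visit, for women of child-bearing potential.
3. Give the screening column an earliest day, so that the age of the screening result is bounded.
4. Have the sponsor reconcile exclusion 2.11 with the schedule by stating when it must be verified relative to the first infusion. What follows from a result, and whether status is checked again before later infusions, is a clinical decision for the sponsor.

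The cost is one urine strip per woman concerned, at a visit that already takes place: at most six strips for six patients, plus one for any replacement patient to whom it applies. No dose, visit, sample size or toxicity criterion changes.
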